5.4.3 Other Efficacy Analyses

The following efficacy analyses are for exploratory purpose only.

5.4.3.1 Platelet count and change from baseline in platelet count at each visit

Platelet count and change from baseline in platelet count will be compared between individual avatrombopag (40 or 60mg) and matching placebo separately within each baseline platelet count cohort at a significance level of $\alpha=0.05$, using the Wilcoxon rank sum test based on observed data. Missing values will not be imputed.

5.4.3.2 Proportion of responders defined as subjects who achieve platelet counts of $\geq 50 \times 10^9/L$, $\geq 75 \times 10^9/L$, or $\geq 200 \times 10^9/L$ at each visit

The number and percentage of responders will be summarized by treatment group within each baseline platelet count cohort at each visit. Missing values will not be imputed.

5.4.3.3 Number of platelet units used per platelet transfusion episode

The average number of platelet units used per platelet transfusion episode will be summarized by treatment group within each baseline platelet count cohort using descriptive statistics for subjects require platelet transfusion.

5.4.3.4 Severity of bleeding event assessed by WHO bleeding score and BARC bleeding scale

The number and percentages of subjects with bleeding events will be summarized by the highest bleeding score and by treatment group within each baseline platelet count cohort, separately for WHO bleeding score and BARC bleeding scale.

5.4.3.5 Proportion of subjects with a WHO bleeding score ≥ 2 after randomization and up to 7 days following an elective procedure

Proportion of subjects with a WHO bleeding score ≥ 2 after randomization and up to 7 days following an elective procedure, will be summarized by treatment group within each baseline cohort, and by overall treatment groups, regardless of the baseline platelet count cohorts.

A 2-sided 95% CI will be constructed by baseline cohort, and for the overall treatment difference (avatrombopag minus placebo) using normal approximation method for the proportion of subjects with the qualified WHO bleeding score.

Subjects with missing WHO bleeding score will be considered as having a WHO bleeding score ≥ 2 in this analysis.

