**16.1.1 Protocol and Protocol Amendments**

The final study protocol is provided on the following pages.

Revisions to V6.0: 31 May 2016 (Amendment 03) Date: V7.0: 02 Dec 2016 (Amendment 04)		
Change	Rationale	Affected Protocol Sections
Sample size reduced from approximately 300 subjects to approximately 200 subjects	After consultation with the FDA, it was decided that the current study has reached adequate enrollment to demonstrate the safety and benefit of avatrombopag in reducing the need for platelet transfusion in subjects with thrombocytopenia and liver disease undergoing an elective procedure.	Synopsis – 
 
• Number of Subjects
 
• Sample Size Rationale
 
 Section 9.3 Section 9.4.3 Section 9.7.2
The secondary endpoint, proportion of subjects with a World Health Organization (WHO) bleeding score $\geq 2$ after randomization and up to 7 days following an elective procedure, will be an exploratory endpoint	Given the rare occurrence of bleeding events (less than expected), this endpoint is better suited as an exploratory endpoint.	Synopsis – 
 
• Secondary Objectives
 
• Exploratory Objectives
 
• Secondary Endpoints
 
• Exploratory Endpoints
 
• Secondary Efficacy Variable Analyses
 
• Exploratory Efficacy Variables
 
 Section 8.2 Section 8.3 Section 9.7.1.1 Section 9.7.1.6

---

Revisions to V5.0: 22 June 2015 (Amendment 02) Date: V6.0: 31 May 2016 (Amendment 03)		
Change	Rationale	Affected Protocol Sections
Clarification to Inclusion Criteria #3: replace the word "change" with the word "increase"	Per FDA request	Synopsis – 

• Inclusion Criteria Section 9.3.1

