4 DETERMINATION OF SAMPLE SIZE

The proposed sample size was based on comparisons of the primary efficacy variable, with the response rate defined as the proportion of subjects who do not require a platelet transfusion or any rescue procedure for bleeding after randomization and up to 7 days following an elective procedure. Based on clinical opinion and the published results of a similar compound in adults with thrombocytopenia associated with liver disease (ELtrombopag EValuated for its Ability to overcome Thrombocytopenia and Enable procedures [ELEVATE] study [Afdahl, 2012])², the response rate in the placebo group is assumed to be 18%. Within each baseline platelet count cohort, a sample size of 100 randomized subjects, 67 subjects for avatrombopag and 33 subjects for placebo, would have greater than 90% power to detect an absolute difference of 35% between the avatrombopag response rate and the placebo response rate assuming 18% response rate for placebo using Fisher's Exact tests with a 2-sided $\alpha=0.05$. The hypothesized treatment group difference was based on platelet count changes found in the Phase 2 study (E5501-G000-202) and dose-response modeling using data from that study and others in the project development. Based on the baseline data in the Phase 2 study and assuming these were projected to be similar for this study, it was anticipated that this study would enroll roughly half of the total number of subjects in each of the 2 baseline platelet count cohorts to make the total sample size of 200 randomized subjects, 133 subjects for avatrombopag and 67 subjects for placebo.

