5.3.5 Handling of Missing Data, Drop-outs, and Outliers

Unless stated otherwise, missing values will be considered as non-responders in responder analyses for all efficacy analyses; observed data will be used in other type of efficacy analyses. Details can be found in [Sections 5.4, Efficacy Analyses](#).

All safety analyses will be performed based on the observed data only.

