5.4.1 Primary Efficacy Analyses

The primary efficacy variable is the proportion of subjects who do not require a platelet transfusion or any rescue procedure for bleeding after randomization and up to 7 days following an elective procedure.

The null hypothesis is that the proportion of subjects not requiring a platelet transfusion or any rescue procedure for bleeding after randomization and up to 7 days following an elective procedure is the same between the avatrombopag and placebo treatment groups. The corresponding alternative hypothesis is that the proportion of subjects not requiring a platelet transfusion or any rescue procedure for bleeding after randomization and up to 7 days following an elective procedure is not the same between avatrombopag and placebo. This hypothesis will be tested separately with each baseline platelet count cohort.

The proportion of subjects not requiring a platelet transfusion or any rescue procedure for bleeding will be tested between the individual avatrombopag treatment group (40 or 60mg) and matching placebo within each baseline platelet count cohort ($<40 \times 10^9/L$ or from 40 to $<50 \times 10^9/L$), each at a significance level of $\alpha=0.05$ using the generalized Cochran Mantel Haenszel (CMH) test adjusting for the risk of bleeding associated with the elective procedure (low, moderate, or high based on Amendment 02 categorization).

- For subjects with platelet count $<40 \times 10^9/L$ at baseline, the treatment comparison will be carried out between the 60 mg avatrombopag treatment group (Group A) versus matching placebo (Group B).
- For subjects with platelet count from 40 to $<50 \times 10^9/L$ at baseline, the treatment comparison will be carried out between the 40 mg avatrombopag treatment group (Group C) versus matching placebo (Group D).

This study will be considered as positive if statistical significance is achieved for primary efficacy endpoints for both baseline platelet count cohorts.

The 95% CI for the proportion of subjects not requiring a platelet transfusion or any rescue procedure for bleeding will be calculated for each treatment group within each baseline platelet count cohort. In addition, the 95% CI for the difference between avatrombopag and matching placebo will also be provided within each baseline platelet count cohort using normal approximation method.

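### SAP 5.4.3.5 uses a normal-approximation CI for WHO grade 2 or higher bleeding, too sparse an endpoint for it: the difference CI can under-cover, collapse to [0, 0], or exclude zero on 4 v 0 events

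*SAP*

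**What the plan says.** SAP 5.4.3.5 summarises WHO bleeding of grade 2 or higher, from randomization to 7 days after the procedure, by treatment group within each cohort and overall. It then specifies: "A 2-sided 95% CI will be constructed by baseline cohort, and for the overall treatment difference (avatrombopag minus placebo) using normal approximation method". It names no continuity correction, no score or exact alternative, and no rule for empty cells. A subject without a WHO score is counted as a bleed, in line with SAP 5.3.5 ("missing values will be considered as non-responders in responder analyses for all efficacy analyses").

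The Amendment 04 entry in the protocol's revision history explains why the endpoint was moved from secondary: "Given the rare occurrence of bleeding events (less than expected), this endpoint is better suited as an exploratory endpoint". SAP section 4 gives the sizes: per cohort, "a sample size of 100 randomized subjects, 67 subjects for avatrombopag and 33 subjects for placebo"; overall, "the total sample size of 200 randomized subjects, 133 subjects for avatrombopag and 67 subjects for placebo". SAP 5.4.3 labels the whole group of analyses: "The following efficacy analyses are for exploratory purpose only".

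**The concern.** The Wald interval needs a reasonable number of events in each arm. The sponsor describes these events as rare, and 2:1 allocation leaves placebo the smaller arm. An arm with no events contributes zero to the estimated variance, so the calculation treats its rate as known to be exactly 0. The interval is then too narrow, and it errs mostly in one direction because the smaller arm is more often the empty one.

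This is the only interval the SAP text names for WHO bleeding, and no test accompanies it. Readers will therefore judge the bleeding difference from it. A handful of events could look like excess bleeding on avatrombopag, or an absence of events could look like certainty.

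There is also an ambiguity. The sentence does not say whether the cohort interval is for the difference or for each arm. SAP 5.4.1 ties the same method to the difference ("the 95% CI for the difference between avatrombopag and matching placebo will also be provided within each baseline platelet count cohort using normal approximation method"), and 5.4.2.1 does likewise, so the difference is the likelier reading.

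**Working it through.** **Inputs.** Arm sizes 67 v 33 and 133 v 67 (SAP 4). The documents give no WHO grade 2 or higher rate, so true rates of 1% to 5% in each arm are assumed (25 pairs). Pairs are written avatrombopag v placebo. Normal approximation is read as the plain unpooled form.

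**The plan's own figure.** SAP 4 claims more than 90% power per cohort for 53% v 18% by Fisher's exact test. Exact enumeration at 67 v 33 gives 92.6%, so the sizes are reproduced.

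**Formula.** d ± 1.96 × √(p1(1−p1)/n1 + p2(1−p2)/n2), where d = p1 − p2.

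**No events.** Both variance terms vanish and the interval is [0, 0]. At a common rate p this has probability (1−p)^(n1+n2):
- per cohort: 0.99^100 = 36.6% and 0.98^100 = 13.3%
- overall: 0.99^200 = 13.4% and 0.98^200 = 1.8%

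For 0/133 v 0/67, Newcombe gives -5.4 to 2.8 points.

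**Events on avatrombopag only.** With x v 0 events the lower limit exceeds zero when x > 3.84 × (1 − x/n1). At x = 3 the right side is 3.67 (n1 = 67) or 3.75 (n1 = 133), so zero is included. At x = 4 it is 3.61 or 3.73, so zero is excluded. Four events are enough at either size, and the placebo sample size plays no part.

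For 4/133 v 0/67:
- Wald: d = 0.0301, SE = √(0.0301 × 0.9699/133) = 0.0148, interval 0.1 to 5.9 points.
- Newcombe: the Wilson limits are 1.18% to 7.48% for 4/133 and 0 to 5.42% for 0/67. Lower limit = 3.01 − √(1.83² + 5.42²) = -2.7; upper limit = 3.01 + 4.47 = 7.5.
- Miettinen-Nurminen: -2.5 to 7.5. Fisher p = 0.30.

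For 4/67 v 0/33: Wald 0.3 to 11.6, Newcombe -5.1 to 14.4, Fisher p = 0.30.

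**Coverage of the nominal 95% interval** (both binomials enumerated, no missing scores):

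| | Cohort, 67 v 33 | Overall, 133 v 67 |
|---|---|---|
| Wald, range over 25 pairs | 63.2% to 99.6% | 73.8% to 97.5% |
| Wald, pairs below 90% | 12 | 4 |
| Wald, 1% v 2% | 72.2% | 73.8% |
| Wald, 1% v 3% | 63.2% | 86.4% |
| Wald, 2% v 4% | 73.7% | 91.7% |
| Wald, 4% v 2% | 93.8% | 96.4% |
| Newcombe, range | 97.4% to 99.8% | 96.1% to 99.0% |
| Miettinen-Nurminen, range | 92.3% to 99.3% | 94.8% to 98.3% |

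The overall 1% v 2% case shows the mechanism. The true difference is -1 point. When placebo has no events, the lowest lower limit the formula can give is about -0.7 (at 1 event on avatrombopag), so the interval always misses. Placebo has no events with probability 0.98^67 = 25.8%, which accounts for nearly all of the 26.2% non-coverage.

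**False exclusion of zero, overall, equal true rates** (nominal 2.5% per side):

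| True rate | 1% | 2% | 3% | 5% |
|---|---|---|---|---|
| Wald wholly above zero | 2.3% | 7.2% | 7.9% | 5.8% |
| Wald wholly below zero | 0.1% | 0.6% | 0.9% | 1.3% |
| Newcombe above | 0.0% | 0.0% | 0.3% | 1.1% |
| Newcombe below | 1.0% | 2.2% | 2.7% | 2.8% |

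Per cohort, Wald lies wholly above zero in 0.3%, 2.3%, 5.2% and 8.2% at the same rates.

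**With missing counted as a bleed.** Assume a fraction m missing in both arms; the analysed rate becomes m + (1−m)p. At m = 2%, 9 of 25 cohort pairs stay below 90% (minimum 80.6%, at 1% v 3%). Overall none do (91.2% to 95.0%), and [0, 0] at a true 1% falls to 0.2%. The overall interval still lies wholly above zero in 7.9% of trials at a true 1% in both arms. At m = 5% no pair is below 90% at either size.

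**Only if the cohort interval is for a single arm:** at n = 33, Wald coverage is 28.2% at a true 1% and 48.6% at 2%. A count of 0/33 would show as [0, 0], against an exact upper limit of 10.6%.

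**The case against.** Five points can be made for leaving the sentence alone.

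- **The rates are assumed.** True, and coverage depends on them. At equal rates the overall coverage never falls below 91.2% on the grid, and all four overall pairs below 90% have the higher rate on placebo. The [0, 0] and 4 v 0 results, however, are arithmetic and need no assumed rate.
- **Missing scores count as bleeds, which thins out the sparsity.** This largely stands for overall coverage and for the collapse. It does not remove the lopsided error or, at 2% missing, the cohort under-coverage.
- **Another variant may be intended.** With a continuity correction, 4 v 0 includes zero (-2.0 to 13.9 points per cohort, -1.0 to 7.0 overall), 0 v 0 does not collapse, and only 2 cohort pairs and 1 overall pair fall below 90%. With a pooled standard error 4 v 0 also includes zero, though 0 v 0 still collapses. The SAP states neither, and programming rules and table shells sit in separate documents. If a variant is meant, the SAP should name it.
- **Newcombe is lopsided the other way,** so it is less likely to flag excess bleeding on avatrombopag. This is so, but its larger tail on the 1% to 5% grid is at most 2.8%, close to nominal, whereas Wald's reaches 7.9% overall.
- **Little rests on it.** This stands. The endpoint is exploratory and untested, and counts and percentages accompany the interval. Bleeding is also tabulated by highest WHO and BARC grade (SAP 5.4.3.4) and as an adverse event of special interest (SAP 5.6.6.1).

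**Conclusion.** The concern holds as a minor point. Read as plain Wald, the specified interval gives [0, 0] on no events and excludes zero on 4 v 0 with Fisher p = 0.30. At equal true rates of 2% to 3% it falls wholly above zero overall about three times as often as its nominal 2.5%. Coverage can be far below 95%, mainly per cohort and mainly when the higher rate is on placebo. The overall difference, the only interval stated without ambiguity, is less affected.

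These sizes rest on true rates of 1% to 5%, the planned arm sizes and, except where stated, no missing scores. The 4 v 0 artefact applies only when the events are on avatrombopag: with 0 v 4, Fisher's p is about 0.01 and Newcombe excludes zero too. The missing-as-bleed rule is pre-specified and is not at issue. No primary or secondary result is touched.

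**What to change.** Change the interval sentence in SAP 5.4.3.5 only. Specify Newcombe or Miettinen-Nurminen 95% intervals for the cohort and overall differences, and Wilson or Clopper-Pearson for any single-arm proportion. State in the same sentence which quantity the cohort interval covers. Keep the missing-as-bleed rule. Optionally, show the number of imputed bleeds by arm and repeat the summary on recorded scores.

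The cost is one sentence and standard software options. Intervals become wider: at 2% in both arms, the mean width rises from 7.7 to 11.1 points overall and from 10.1 to 18.7 points per cohort (Wald to Newcombe). The SAP would also carry two methods for differences in proportions, since 5.4.1 and 5.4.2.1 keep the normal approximation. A clause giving event sparsity as the reason would cover that.

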### 8.3 EXPLORATORY OBJECTIVES

The exploratory objectives of the study are:

- To characterize the pharmacokinetics and the relationship between avatrombopag plasma concentrations and platelet count using the population approach
- To characterize platelet count changes from baseline, the extent of platelet transfusion use, evaluate the incidence of bleeding events, and assess the severity of any bleeding events (revised per Amendment 04)
- To assess the health economic impact associated with minimizing the need for platelet transfusions and any rescue procedure for bleeding associated with an elective procedure

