3.1.3 Exploratory Objective(s)

The exploratory objectives of the study are:

- To characterize the pharmacokinetics (PK) and the relationship between avatrombopag plasma concentrations and platelet count using the population approach
- To characterize platelet count changes from baseline, the extent of platelet transfusion use, evaluate the incidence of bleeding events, and assess the severity of any bleeding events
- To evaluate the health economic impact associated with minimizing the need for platelet transfusions and any rescue procedure for bleeding associated with an elective procedure

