5.2 STUDY SUBJECTS

5.2.1 Definitions of Analysis Sets

Full Analysis Set (FAS): The FAS is the group of all subjects who are randomized into the study.

Per Protocol Analysis Set (PP): The PP is the group of all randomized subjects who receive protocol-assigned study drug and do not meet any of the following criteria:

- Baseline platelet count of $>50 \times 10^9/L$
- Subjects who were enrolled in the study despite not being planned for transfusion even in the event of no significant increase of platelet count
- Taking prohibited prior medications or prior transfusion
- Presence of significant bleeding at baseline
- Did not have a protocol permitted procedure on Day 8 - 15
- Received dose different from the intended dose
- Received $<80\%$ of the total dose or received $>40\%$ of total dose without food
- No elective procedures or elective procedure outside day 8-15
- Subject received platelet transfusion before knowing V4 platelet count
- Subject refused platelet transfusion

Subjects who met any of the criteria listed above will be excluded from the PP due to possible introduction of bias.

Safety Analysis Set: The Safety Analysis Set is the group of subjects who receive at least one dose of study drug and have at least one post dose safety assessment.

The number (percentage) of subjects in each analysis set will be summarized by treatment groups using descriptive statistics. The summaries for FAS and PP will be based on subjects “as randomized”. The summary for Safety Analysis Set will be based on subjects “as treated”.

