5.4.1.1 Sensitivity Analysis

The following analyses will be considered as sensitivity analyses:

- PP analysis: The same primary efficacy analyses described in [Section 5.4.1](#) will be repeated based on the PP analysis set.
- Observed case: The same primary efficacy analyses described in [Section 5.4.1](#) will be repeated based on observed data. Subjects with missing information about the primary efficacy outcome will be excluded from this analysis.
- Fisher's exact Test: The same primary efficacy analyses described in [Section 5.4.1](#) will be carried out using Fisher's exact test.
- Modified primary efficacy endpoint: Proportion of subjects who do not require a platelet transfusion after randomization and up to 7 days following an elective procedure. This efficacy endpoint will be analyzed using the same approach as primary efficacy analysis using FAS

Additional sensitivity analyses may also be explored, if deemed appropriate.

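### SAP 5.4.3.5 counts every missing WHO score as a grade 2 or worse bleed, with no observed-case result beside it; for a rare event, imputed cases could be half or more of those reported

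*SAP*

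**What the plan says.** SAP 5.4.3.5 summarizes the proportion of subjects with WHO grade 2 or worse bleeding, from randomization to 7 days after the procedure, by arm within each cohort and overall. It gives a 95% normal-approximation interval by cohort and for the overall difference. Its missing-data rule is: "Subjects with missing WHO bleeding score will be considered as having a WHO bleeding score" of 2 or more. Efficacy analyses use the full analysis set, and "The FAS is the group of all subjects who are randomized into the study" (SAP 5.2.1).

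Amendment 04 made the endpoint exploratory: "Given the rare occurrence of bleeding events (less than expected), this endpoint is better suited as an exploratory endpoint" (Protocol, revision history). The matching objective is to "evaluate the incidence of bleeding events, and assess the severity of any bleeding events" (SAP 3.1.3; Protocol 8.3). SAP 5.4.3 opens with "The following efficacy analyses are for exploratory purpose only".

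The one observed-case analysis in the SAP is for the primary endpoint: "Subjects with missing information about the primary efficacy outcome will be excluded from this analysis" (SAP 5.4.1.1). Two other sections report bleeding. SAP 5.4.3.4 counts subjects by highest WHO and BARC score; it has no missing-data rule, so the observed-data default of SAP 8.2 applies. SAP 5.6.6.1 summarizes WHO grade 2 to 4 bleeding adverse events in the Safety Analysis Set, on observed data.

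**The concern.** Missing-equals-failure distorts little when failure is common. The primary endpoint assumes 18% response on placebo, so 82% fail anyway. When the event is rare, a few missing scores can equal or outnumber the real events, and the interval treats them as observed bleeds.

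At the planned sizes in SAP 4 (67 v 33 per cohort), one missing score adds 1/33 = 3.0 points to a placebo cohort's bleeding rate and 1/67 = 1.5 points to an avatrombopag cohort's. The rule is also not reliably conservative: if more placebo subjects have missing scores, it favours avatrombopag.

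Some missingness is foreseeable. Every randomized subject is in the analysis, and subjects removed from the study may not be replaced (Protocol 9.5.5). Early discontinuers are directed to Visit 4 and Visit 6 assessments, and their procedure may happen outside the study (Protocol 9.3.3; Table 5 notes b and c). Visit 5, the 7-day visit, is not named there. The SAP does not say which visits must be absent for a score to count as missing. Nor does it say how this endpoint treats a subject who has no procedure and so no 7-day window; the visit windows in SAP 8.1 are for by-visit summaries.

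**Working it through.** **The plan's own figure.** None is stated for this endpoint. The only power claim is for the primary endpoint (53% v 18%, 67 v 33, Fisher's exact test, two-sided 0.05, above 90%). Exact enumeration gives 92.6%, so it reproduces; it does not bear on this point.

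**Inputs.** Planned arms are 133 v 67, total 200 (SAP 4). The true rate b and missing fraction m are in neither document, so both are assumptions shown as ranges. Missingness is taken as independent of bleeding.

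**Step 1, inflation.** Reported incidence = m + (1-m)b.
- b = 2%, m = 5%: 0.05 + 0.95 × 0.02 = 6.9%.
- b = 5%, m = 1%: 0.01 + 0.99 × 0.05 = 5.95%.

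**Step 2, imputed share of reported events** = m / [m + (1-m)b]:

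| b | m = 1% | 2% | 3% | 5% | 10% |
|---|---|---|---|---|---|
| 1% | 50% | 67% | 76% | 84% | 92% |
| 2% | 34% | 51% | 61% | 72% | 85% |
| 3% | 25% | 40% | 51% | 64% | 79% |
| 5% | 17% | 29% | 38% | 51% | 69% |
| 10% | 9% | 17% | 24% | 34% | 53% |

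**Step 3, break-even.** The share passes one half when m > (1-m)b, that is m > b/(1+b): 1.0%, 2.0%, 2.9%, 4.8% and 9.1% for b = 1%, 2%, 3%, 5% and 10%. At b = 2% and m = 2%, 200 × 0.02 = 4 imputed events stand beside 196 × 0.02 = 3.9 observed ones.

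**Step 4, unequal missingness, avatrombopag minus placebo.**
- True 2% in both arms, missing 5% v 10%: 0.069 - (0.10 + 0.90 × 0.02) = 0.069 - 0.118 = -4.9 points. The normal-approximation 95% interval at 133 v 67 is -13.7 to 3.9.
- True 2% in both arms, missing 3% v 6%: 0.0494 - 0.0788 = -2.9 points (-10.4 to 4.5).
- A real difference hidden: true 2% v 4%, missing 5% v 3%: 0.0690 - (0.03 + 0.97 × 0.04) = 0.0690 - 0.0688 = +0.02 points, against a true -2.0.

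**Step 5, equal missingness.** The difference is only multiplied by (1-m). The ratio moves toward 1: for true 2% v 4%, 0.50 becomes 0.72, 0.78 and 0.87 at m = 3%, 5% and 10%.

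**The case against.** The case for leaving the rule alone has real strength.

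- **The convention is consistent.** SAP 5.3.5 treats missing values as the unfavourable outcome in responder analyses unless stated otherwise. That makes the rule a choice, not a mistake. It is not uniform, however: the exploratory platelet-responder summary in SAP 5.4.3.2 leaves missing values unimputed.
- **Bleeding is reported elsewhere.** A reader might infer that the incidence objective rests on 5.4.3.5 alone. It does not. SAP 5.4.3.4 shows observed highest scores, and SAP 5.6.6.1 covers the same WHO grades. Protocol 9.5.4.3 also requires every WHO grade 2 to 4 bleed to be entered as an adverse event and reported through SAE procedures. The limit is that 5.4.3.4 is not confined to the 7-day window, and 5.6.6.1 uses coded adverse events as treated, to 30 days after the last dose. Neither gives a difference or interval.
- **Withdrawal is not the same as a missing score.** A reader might infer that leaving the study is scored as a bleed. Bleeding is assessed at Visits 2 to 6 (Protocol Table 5), and discontinued subjects are still scheduled for Visits 4 and 6, so many would have scores.
- **Little hangs on it.** The endpoint is exploratory, with no planned test and no alpha. In the larger example above the interval includes zero, so it would not support a claim that avatrombopag changes bleeding.

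All four limit the point. None supplies an observed-case estimate for the 7-day endpoint or says when its score is missing.

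**Conclusion.** The point holds conditionally. If the missing fraction is similar to or larger than the true event rate, imputed subjects make up about half or more of the reported grade 2 or worse events. Unequal missingness can then create or hide a difference of a few points in the only planned difference and interval for this endpoint.

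It is tempting to go further and say that the reported incidence mostly measures missing data, or that any arm difference follows dropout. The documents do not support either statement. They call bleeding rare but give no rate, and they give no missing-score rate. With near-complete follow-up the imputed share is modest (17% at b = 5%, m = 1%; 34% at b = 2%, m = 1%), and with equal missingness a true difference shrinks only by the factor (1-m).

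The sizes rest on assumed b and m and on missingness unrelated to bleeding. This is a cheap improvement, not a threat to the trial's conclusions.

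**What to change.** In SAP 5.4.3.5:

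1. Report the observed-case proportion with WHO grade 2 or worse to 7 days after the procedure, with the difference and 95% interval.
2. Show the number of imputed subjects in each arm, by cohort and overall.
3. Keep the missing-equals-bleed result, labelled as a worst-case analysis.
4. State when a score counts as missing: which visits are needed, and how subjects without a procedure are handled.

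The cost is SAP wording and an extra table row. The downside is that an observed-case result rests on subjects with data, which the retained worst-case row addresses.
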